4. SAMPLE SIZE CALCULATION

In the ANRS 146 OPTIMAL trial [Levy et al.], of late presenters, the proportion of patients with severe morbidity (new adverse drug event (ADE), other HIV related diseases, serious non-AIDS events, IRIS and death) was estimated at 12.2% per year in the boosted PI arm. The virological failure was estimated at 20% at week 48 in the DRV/r group of the IMEA 040 DATA study (Slama L et al) that recruited a similar population. As a few subjects will meet more than one of these criteria, we assumed a cumulative probability of failure at 25% at 48 weeks in the PI regimen group.

A total of 404 evaluable subjects, randomized in a 1:1 ratio to 2 treatment groups (202 subjects per treatment group), achieves at least 80% power to detect a non-inferiority margin of 1.606 in the hazard ratio, which corresponds to a 12% difference in the cumulative probability of failure rate between INI-based regimen group (37%) and PI-based regimen group (25%), with 97 events required. The sample size and power calculation assume that the cumulative probability of failure is 25% for the PI regimen group and 23% for the INI-based regimen group (i.e. the expected hazard ratio is 0.909), using a non-inferiority margin of 1.606 in hazard ratio and a two-sided 95% confidence interval (CI). The sample size and power calculation were made using the statistical software package nQuery Advanced, non-inferiority testing of two survival curves using cox regression module (Version 8.1.2.0).

With an estimated ~7.5% drop off rate/year, we plan to enrol 220 subjects per group to ensure we have sufficient power for this per-protocol analysis.

Superiority of INI-based regimen group versus PI-based regimen group will be evaluated after the non-inferiority is established. With an ITT analysis, 440 subjects and 78 events, a two-sided log-rank test at an alpha level of 0.05 will achieve at least 80% power to detect a 50% reduction in hazard rate in INI-based regimen (i.e. the hazard ratio is 0.5). A 50% reduction in hazard rate means that INI-based regimen could decrease the risk by 11.6% (25% for PI- vs 13.4% for INI- based regimen).

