10.1.3 Quality of life (EQ-5D-3L questionnaire) and HIV Symptoms index

Endpoints

The endpoints are:

- Change from baseline in health status score ranging from 0 to 100 (100 being best quality of life) and in each of the 5 dimensions of the EQ-5D-3L quality of life questionnaires (mobility, self-care, usual activities, pain/discomfort and anxiety/depression). Each dimension has 3 levels: 1=no problems, 2=some problems, and 3=extreme problems.
- Change from baseline in HIV symptoms index score over time. HIV Symptoms Index questionnaire is consisted of 20 selected symptoms. Each symptom has 5 levels: 0=I do not have this symptom 1=It doesn't bother me 2=It bothers me a little 3=It bothers me 4=It bothers me a lot. The HIV Symptom Index score is the sum of frequency ratings for the 20 selected symptoms; the score could range from 0 to 80.

Descriptive statistics and graphical representation

The analyses will be performed with the mITT population who complete the baseline questionnaire and least one of the follow-up questionnaires.

Data for health status score and HIV Symptoms index will be summarised by mean and standard error. The evolution of health status score and HIV Symptoms index will be described by boxplots for each treatment group at each time point.

Data for the 5 dimensions will be summarised with number and percentages per class and Bar plotted will also be generated for each of the 5 dimensions.

The number of participants with data available at each time point will also be reported.

Statistical methodology

The changes from baseline in health status score will be compared between the two treatment groups using mixed models for repeated measures with random intercept and slope and spatial power covariance structure due to unequal time intervals between visits, adjusted for country/group of neighbouring countries and baseline CD4 cell counts (<50 or $\geq 50/\mu\text{L}$). The model will include treatment group, time, interaction between treatment group and time, country/group of neighbouring countries and baseline CD4 cell counts (<50 or $\geq 50/\mu\text{L}$). Time will be modelled as categorical variables.

The distribution of each of the 5 dimensions (mobility, self- care, usual activities, pain/discomfort and anxiety/depression), will be compared between the two treatment groups at each timepoint using Chi-square test

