The changes from baseline in Symptom index score will be compared between the two treatment groups using mixed models for repeated measures with random intercept and slope and spatial power covariance structure due to unequal time intervals between visits, adjusted for country/group of neighbouring countries and baseline CD4 cell counts (<50 or \geq 50/ μ L). The model will include treatment group, time, interaction between treatment group and time, country/group of neighbouring countries and baseline CD4 cell counts (<50 or \geq 50/ μ L). Time will be modelled as categorical variables. All p-values will be two-tailed, with a significant level of 0.05.

10.1.4 discontinuation or modification of study medication due to insufficient virological response or resistance mutation development before week 48

Endpoints

The endpoint is the proportion of patients with discontinuation or modification of study medication due to insufficient virological response or resistance mutation development before week 48.

Descriptive statistics and graphical representation

The analyses will be performed with the mITT population and DPS1. Data will be summarised with the number and percentage of participants with discontinuation or modification of study medication due to insufficient virological response or resistance mutation development through week 48. The list of patients with the event of interest will be reported in a table, including the reasons for discontinuation or modification of study medication.

Statistical methodology

The percentage of patients with discontinuation or modification of study medication due to insufficient virological response or resistance mutation development will be estimated by the number of patients with the event of interest divided by the total number patients in ITT population.

The effect of study treatment on the proportion of patients with discontinuation or modification of study medication due to insufficient virological response or resistance mutation development through week 48 will be assessed using a logistic regression model with treatment group and adjustments for stratification factor (country/group of neighbouring countries and baseline CD4 cell counts (<50 or \geq 50/ μ L)). An adjusted odds ratio (OR) and the associated 95% Confidence Interval (CI) will be calculated.

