Week	Mobility			Self- care		
	Integrase Inhibitor	Protease Inhibitor	P-value between groups	Integrase Inhibitor	Protease Inhibitor	P-value between groups
0 1=no problems, 2=some problems, 3=extreme problems	n/N (%)	n/N (%)		n/N (%)	n/N (%)	
4 1=no problems, 2=some problems, 3=extreme problems						
8 1=no problems, 2=some problems, 3=extreme problems						
12 1=no problems, 2=some problems, 3=extreme problems						
24 1=no problems, 2=some problems, 3=extreme problems						
36 1=no problems, 2=some problems, 3=extreme problems						
48 1=no problems, 2=some problems, 3=extreme problems						
RR (95% CI) from baseline to W4						
RR (95% CI) from baseline to W8						
RR (95% CI) from baseline to W12						
RR (95% CI) from baseline to W24						
RR (95% CI) from baseline to W36						
RR (95% CI) from baseline to W48						

TABLE 11: QUALITY OF LIFE DIMENSIONS: USUAL ACTIVITIES AND PAIN/DISCOMFORT

Week	Usual activities			Pain/discomfort		
	Integrase Inhibitor	Protease Inhibitor	P-value between groups	Integrase Inhibitor	Protease Inhibitor	P-value between groups
0 1=no problems, 2=some problems, 3=extreme problems	n/N (%)	n/N (%)		n/N (%)	n/N (%)	
4 1=no problems, 2=some problems, 3=extreme problems						
8 1=no problems, 2=some problems, 3=extreme problems						
12 1=no problems, 2=some problems, 3=extreme problems						
24 1=no problems, 2=some problems, 3=extreme problems						
36 1=no problems, 2=some problems, 3=extreme problems						
48 1=no problems, 2=some problems, 3=extreme problems						
RR (95% CI) from baseline to W4						
RR (95% CI) from baseline to W8						
RR (95% CI) from baseline to W12						
RR (95% CI) from baseline to W24						
RR (95% CI) from baseline to W36						
RR (95% CI) from baseline to W48						

TABLE 12: QUALITY OF LIFE DIMENSIONS: ANXIETY/DEPRESSION

Week	Anxiety/depression		
	Integrase Inhibitor	Protease Inhibitor	P-value between groups
n/N (%)	n/N (%)		
0 1=no problems, 2=some problems, 3=extreme problems			
4 1=no problems, 2=some problems, 3=extreme problems			
8 1=no problems, 2=some problems, 3=extreme problems			
12 1=no problems, 2=some problems, 3=extreme problems			
24 1=no problems, 2=some problems, 3=extreme problems			
36 1=no problems, 2=some problems, 3=extreme problems			
48 1=no problems, 2=some problems, 3=extreme problems			
RR (95% CI) from baseline to W4			
RR (95% CI) from baseline to W8			
RR (95% CI) from baseline to W12			
RR (95% CI) from baseline to W24			
RR (95% CI) from baseline to W36			

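### SAP 10.1.3 names change from baseline as the endpoint for the five EQ-5D-3L dimensions but tests only their unordered distribution at each visit; an ordinal model that uses the baseline level is a cheap improvement

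*Combined protocol and SAP*

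**What the plan says.** SAP 10.1.3 lists as an endpoint the change from baseline in the health status score and "in each of the 5 dimensions of the EQ-5D-3L quality of life questionnaires". The scale is ordered: "Each dimension has 3 levels: 1=no problems, 2=some problems, and 3=extreme problems". The analysis is limited to mITT patients with a baseline questionnaire and at least one later one.

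For the dimensions, the descriptive plan is that "Data for the 5 dimensions will be summarised with number and percentages per class". The inferential plan is one sentence: "The distribution of each of the 5 dimensions", which the SAP then lists by name, "will be compared between the two treatment groups at each timepoint using Chi-square test". For the section as a whole, "All p-values will be two-tailed, with a significant level of 0.05".

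The shells of Tables 10 to 12 have a between-group p-value column covering week 0 to week 48, and rows such as "RR (95% CI) from baseline to W48" for every post-baseline visit.

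Protocol 9.3.3 and 9.7 (the same in v1.5 and v5.0) plan multiple imputation with five datasets, Rubin's rules and a GEE for quality of life at week 48. SAP 5.3 keeps multiple imputation for patient-reported outcomes.

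**The concern.** Three things do not fit together. The endpoint is change, but a table of arm by level at one visit contains no baseline information. The scale is ordered, but a Pearson chi-square test treats its levels as unordered labels. The shells report a relative risk from baseline, but 10.1.3 gives no model for one and no rule for reducing three levels to two.

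Quality of life and functional status is a listed secondary outcome. Left as it is, the analyst of an open-label trial has to choose the cut-point and the model behind the relative risks without a written rule. The p-values that are specified leave information unused that the trial has already collected.

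**Working it through.** **1. Patients per arm, and the plan's own figure.** The documents give no power or effect size for the dimensions, so the sample size section is used only for the number per arm, with patients "randomized in a 1:1 ratio to 2 treatment groups".
- Margin: ln(0.63)/ln(0.75) = 1.606. Expected hazard ratio: ln(0.77)/ln(0.75) = 0.909.
- Events: 4 × 7.85 / [ln(1.606/0.909)]² = 97.
- Patients: 97 / 0.24 = 404, or 202 per arm. Dropout: 202 / (1 − 0.075) = 219, planned as 220.

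The stated figures reproduce. I use 202 and 220 per arm, with 190 as an assumed lower value.

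**2. The three outcomes of SAP 10.1.3 side by side.**

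| Outcome | Endpoint | Method | Uses baseline | Adjusted for strata |
|---|---|---|---|---|
| Health status score | change | mixed model on change | yes | yes |
| HIV symptom index | change | mixed model on change | yes | yes |
| Five dimensions | change | chi-square per visit | no | no |

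A log-link GEE that yields relative risks is described only for the CD4 thresholds (7.2.5) and for binary urine parameters (note to Table 16). Nothing says how chi-square tests are to be pooled over imputed datasets.

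**3. Order.** Take 150/60/10 against 125/80/15 patients in levels 1/2/3. The chi-square statistic is 6.13 on 2 df, p = 0.047. Permuting the three columns gives exactly the same result.

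**4. Power for a consistent shift.** For 80% power at 5%, the noncentrality needed is 7.85 on 1 df and 9.63 on 2 df; 9.63/7.85 = 1.23. Simulation used 40,000 tables per setting, comparing the Pearson chi-square with the tie-corrected Wilcoxon test, which is close to the proportional-odds score test. All level rates are assumptions. With 220 per arm and a common odds ratio of 1.75:

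| Control levels 1/2/3 | Chi-square | Ordinal test |
|---|---|---|
| 79/20/1% | 48% | 59% |
| 68/30/2% | 63% | 73% |
| 55/40/5% | 73% | 82% |
| 45/45/10% | 77% | 85% |

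Over odds ratios of 1.5 to 2.0 and both 202 and 220 per arm, the gain runs from about 4 to 11 points. At 190 per arm, 60/34/6% against 72/25/3% gives about 63% v 72%, and 55/38/7% against 67/29/4% gives about 60% v 70%.

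**5. Adding the baseline level.** Here the assumed shift is 0.3 SD on a latent scale, with 220 per arm and 2,500 runs (standard error near 70% power: √(0.7 × 0.3/2,500) ≈ 0.9 points).

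| Baseline correlation | Chi-square | Wilcoxon | Wilcoxon stratified by baseline level |
|---|---|---|---|
| 0.3 | 57% | 66% | 66% |
| 0.5 | 57% | 68% | 73% |
| 0.7 | 56% | 66% | 78% |

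With no true difference, all three tests rejected in about 5% of runs.

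**6. Rare level 3.** The expected count per arm is n × pooled rate. It falls below 5 under 5/220 = 2.3% or 5/202 = 2.5%. Simulated type I error of the chi-square test:

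| Level-3 rate | 220 per arm | 202 per arm |
|---|---|---|
| 0.5% | 3.4% | 3.3% |
| 1% | 4.2% | 3.9% |
| 2% | 4.8% | 4.7% |
| 3% | 5.0% | 4.9% |

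**7. The reverse case.** With 55/40/5% against 60/30/10% and 220 per arm, more patients in one arm are at both extremes. The chi-square test has 68% power and the rank test 8%.

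**The case against.** The case for leaving the plan alone is a fair one. Under randomisation, a comparison of arms at a single visit is unbiased without the baseline. The chi-square test makes no assumption about the shape of the difference, and step 7 shows that this can matter a great deal. The shells already show counts and percentages per level. The relative-risk rows resemble those of Table 5, so the log-link GEE of 7.2.5 may have been intended. The protocol's GEE sentence does not name the dimensions.

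Most of this stands, and it limits the point. It does not supply a cut-point or model for the relative risks, nor a test of the stated endpoint.

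Three stronger readings are tempting, and the documents do not support them.
- A reader might infer that the test fails when extreme problems are rare. The documents give no rate for that level, and at assumed rates of 0.5 to 1% the test is conservative, at 3.3 to 4.2%. False positives do not increase.
- A reader might infer that the chi-square test is always the weaker choice. That holds only for a consistent shift.
- A reader might infer that the quality-of-life endpoint as a whole is poorly analysed. The health status score and the symptom index both have adjusted repeated-measures models on change.

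**Conclusion.** This is a cheap improvement to a secondary analysis. It follows from the text alone that the stated test does not analyse change from baseline, ignores the order of the levels and the stratification factors, and does not match the relative-risk rows in the shells. It also follows that 10.1.3 has no rule for sparse levels, although 10.1.1 and 10.1.4 fall back on Fisher's exact test when a group has no events.

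The size rests on assumed level rates, shifts and correlations: roughly 4 to 11 points of power for a consistent shift, and 16 to 23 points over the chi-square test when baseline level is also used and correlates at 0.5 to 0.7 with outcome (73 − 57 and 78 − 56, the latter 22.6 before rounding). These figures come from rank tests at one visit; the proposed GEE itself was not simulated. The primary conclusion, the health status score and the symptom index are unaffected.

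**What to change.** In SAP 10.1.3, replace the chi-square tests by one proportional-odds GEE per dimension, with arm, visit, arm by visit, baseline level, country group and baseline CD4 group. Fit it in each imputed dataset and combine by Rubin's rules, as SAP 5.3 and the protocol imply. Report the common odds ratio with its 95% CI at week 48 as the between-arm result, and keep the other visits descriptive.

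State in advance a level-3 rate, pooled over arms, below which levels 2 and 3 are merged and a binary logistic GEE is used. About 2.5% would match the expected-count limit in step 6.

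In Tables 10 to 12, replace the relative-risk rows by this odds ratio and delete the week-0 p-value. Keep n (%) per level, so that a non-monotone pattern can be seen.

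The cost is SAP wording and three table shells. No new data or visits are needed, the software already named can fit the models, and SAP 5.1 allows updates before sign-off. The downside is reliance on proportional odds, which would hide a difference like that in step 7 if only the odds ratio were read.

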Appendix

Study Protocol and SAP for: [name], [name], [name], [name], [name] et al. **Integrase versus protease inhibitor therapy in advanced HIV disease: The Late Presenter Treatment Optimization (LAPTOP) Randomized Trial**

All documents are for the LAPTOP Study

- 1. Study Protocol v1.5** (08 Jan 2019)
- 2. Study Protocol v5.0** (11 March 2024)
- 3. Statistical Analysis Plan (SAP) v0.3** (22.11.2023)

Changes in the protocol, which was initially approved by the ethics committee (UK), are summarized on page 2-13

Protocol v1.4 to v1.5 (UK only)

This amendment was only in the UK. EU territories initiated on Protocol v1.5 or later.

1. A change of vendor from Covance to ACM Global for the shipment and storage of resistance samples for deep sequencing. This change has also been incorporated into the patient information sheet and informed consent form. Updates to other addresses have also been incorporated.
2. Addition of a weight assessment at week 24 and 48 in the schedule of assessment table. This addition has been included due to scientific evidence that the IMPs used for the study may have a minor effect on patient's weight.
3. Section 6.1.3 required clarification regarding treatment switching
4. Update to one of the secondary outcomes which required additional wording regarding resistance mutations at baseline as patients may switch treatment due to resistance testing results or discontinue medication completely. Although this is not new, it should have been incorporated into the outcome in the previous versions of the protocol.

Protocol v1.5 to v2.0

Comparative table with description of change and rationale for change to the protocol from version 1.5 to version 2.0 (Substantial Amendment 2)

Change No.	Description of Change	Rationale for Change
1.	Study Synopsis- Treatment Arm 2 is referred to as the “comparator arm” to Treatment Arm 1.	This wording was added to ensure that the naming of treatment arm 2 is consistent with how it is described in the Development Safety Update Report.
2.	Section 1.2.1- “Urticaria” has been added as a new uncommon side effect of Biktarvy® and “Changes in Serum Creatinine” and “Changes in Billirubin” contains stability data of up to week 96 (previous data went up to week 48).	These changes reflect the updates contained in the latest version of the Reference Safety Information for Biktarvy® (02 April 2020)

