6.1.3 Resistance Testing and Results

Resistance test results obtained at screening may influence randomisation.

If resistance data of the RT, protease (Table 1 and 2), or integrase gene as described below become available after screening but before randomisation patients should not be randomised (and will be seen to be screen failures).

If data becomes available after randomisation, patients may be considered to switch to the other treatment arm at the investigator's discretion in the following scenarios:

1. Patients randomised to the DRV arm may be considered to switch to the BIC arm only if they have any of the resistance mutation patterns as described in Table 1. In these patients, only TAF and FTC would have full ARV activity. The decision should be made by the investigator after consultations with the LAPTOP study team.

Table 1: Resistance mutation patterns leading to intermediate or high-level resistance against DRV.

Resistance	Mutation pattern ²¹												
	Darunavir	V32I	L33F	K43T	M46I	I47V	I54L/M	G73T/S	L76V	V82A	I84V	L89V	L90M
Intermediate						L							+
Intermediate		+				L	T			+			+
Intermediate				+					+		+		
High	+		+	+	+	M			+				+
High	+	+		+	+	M			+				+
High	+					M	S			+	+	+	+

2. Patients randomised to the DRV or BIC arm may be considered to remain in their treatment arm or to switch to an alternative regime (e.g. PI +INI) only if they have any of the resistance mutation pattern as described in Table 2. Table 2 describes RT inhibitor associated resistance mutation pattern, in which intermediate or high-level resistance against FTC and TFV has to be expected. In these situations, only DRV or BIC would have full ARV activity. The decision to

remain on therapy or to switch should be made by the investigator after consultations with the LAPTOP study team.

Table 2: Resistance mutation patterns leading to intermediate or high-level resistance against FTC or tenofovir disoproxil fumarate (TDF).

Resistance		Mutation pattern									
FTC	TDF	M41L	E44D	K65R	D67N	T69D	K70R	M184V/I	L210W	T215Y	K219N/Q
High	Interm	+						V	+	+	
High	Interm				+		+	V		+	Q
High	Interm	+			+			V	+	+	
High	Interm			+				V			
High	Interm			+				I			
High	High	+	+		+				+	+	
High	High	+	+		+	+		V	+	+	
High	High	+	+		+			V	+	+	N

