However, specifically regimens containing integrase inhibitors (INI) are promising candidates for treatment combinations in patients with CD4 cell counts $<200/\mu\text{l}$ due to their antiviral activity and rapid decline of viral load, beneficial side-effect profile and metabolism pathways compared to other regimens. Also, integrase inhibitors such as dolutegravir (DTG) and bictegravir (BIC/B) have high genetic barriers, thereby preventing resistance mutation development and ensuring sufficient antiviral activity in case of pre-existing mutations against nucleosides (Demarest *et al.*, 2018). Therefore, in cases when needs ART to be initiated before genotypic testing results are available, current European AIDS Clinical Society (EACS) Guidelines (EACS Treatment Guidelines 9.0) recommend to include a drug with a high genetic barrier to resistance in the first-line regimen (e.g. PI or DTG).

We therefore propose a strategic clinical trial to compare an INI containing regimen versus a boosted PI regimen in patients with advanced HIV-infection. We aimed to demonstrate the non-inferiority of an INI containing regimen [bictegravir (B) /emtricitabine (F) /tenofovir alafenamide (TAF) QD] versus a boosted PI regimen [darunavir (D) /cobicistat(C) /emtricitabine (F) /tenofovir alafenamide (TAF) QD] in patients with advanced HIV infection. The superiority of the INI-based treatment group over the PI-based treatment group will be assessed in the event that non-inferiority is established.

This Statistical Analysis Plan (SAP) details the different populations of analysis and the statistical methodology that will be used to analyse the data. It describes the efficacy and safety variables and anticipated data transformations and manipulations, and other details of the analyses not provided in the study protocol. The analyses described are based upon the clinical study protocol Version 2.0 dated 16 June 2020. This SAP will be validated and signed before the primary endpoint analysis is performed.

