2.2.2 Secondary endpoints/outcomes

Secondary endpoints/outcomes included:

- Cumulative incidence of the composite primary endpoint at week 48
- Proportion of patients with HIV-RNA viral load <50 copies/mL at week 24, 36, 48
- HIV-1 drug resistance at confirmed virological failure [Time Frame: Through study completion, an average of 1 year]
- Time to reach CD4 count >200/ μ L (first measurement)
- Proportion of patients with CD4 cell count < 200 μ L and < 350 μ L at week 4, 8, 12, 24, 36, 48
- CD4/CD8 ratio at week 4, 8, 12, 24, 36, 48
- Incidence of IRIS in the two arms through week 48
- Incidence and duration of hospitalisation or rate of relapse of specific opportunistic infection (OI) or bacterial infection (BI) through week 48
- Number and proportion of participants with Grade 2, 3 and 4 adverse events (AEs), treatment-related AEs, AEs leading to the study drug discontinuation, and death through week 48
- ART and OI/BI treatment changes and dose modifications due to toxicities and DDI with ART, and IRIS through week 48
- Healthcare resource use, including total inpatient days and emergency room visits through week 48
- QOL and functional status outcomes, including overall self-reported QOL and functional status compared in the two groups at week 48
- Discontinuation or modification of study medication due to insufficient virological response, resistance mutations at baseline, or resistance mutation development before week 48

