The analyses will also be performed separately for each component of the endpoint (insufficient virological response and resistance mutation development). If no events were observed in a group, the comparison will be made using Fisher's exact test.

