Mean (95% CI) difference from baseline to week 48			

TABLE 7: SAFETY

	Integrase inhibitor (N=XXX) Person-Year (P-Y): XXX.X			Protease inhibitor (N=XXX) Person-Year (P-Y): XXX.X			P-value
	N of events	N of pts (%)	Incidence rate/100 p-y	N of events	N of pts (%)	Incidence rate/100 p-y	
Any adverse events (AEs : grade ≥2)							
Grade 2							
Grade 3							
Grade 4							
Grade unknown							
Grade 3 or 4 AE							
Drug related AEs							
Drug related grade 3/4 AEs							
dress syndrom (rash)							
IRIS							
IRIS-Kaposis sarcoma							
PML-IRIS requiring hospitalisation							
progressive rash							
transaminitis							
worsening symptoms of Progressive multifocal leukoencephalopathy							
....							
....							
AE leading to the study drugs interruption							
Serious adverse events (SAE)							
Laboratory toxicities							
Death							

TABLE 8. OTHER SECONDARY ENDPOINTS

	Integrase Inhibitor	Protease Inhibitor	Adjusted OR	P-value
	N=XXX	N=XXX	(95% CI)	
Percentage of patients with HIV drug resistance mutations among those with virological failure				
Proportion of patients with ART treatment changes due to toxicities and/or DDI with ART, and/or IRIS through week 48 - due to toxicities - due to DDI - due to IRIS				
Proportion of patients with with health care resource use, including total inpatient days and emergency room visits through week 48				
Proportion of patients with discontinuation or modification of study medication due to insufficient virological response or resistance mutations development before week 48 - for insufficient virological response - resistance mutations development				
Proportion of patients for whom there is a difference in the list of mutations (Stanford list last available version) detected by deep sequencing compared with those detected by population sequencing				

TABLE 9: EVOLUTION OF QUALITY OF LIFE (HEALTH STATUS SCORE) AND HIV SYMPTOMS INDEX

Week	QOL : health status score			HIV Symptoms index score		
	Integrase Inhibitor	Protease Inhibitor	P-value between groups	Integrase Inhibitor	Protease Inhibitor	P-value between groups
	Mean (SD)	Mean (SD)		Mean (SD)	Mean (SD)	
0						
4						
8						
12						
24						
36						
48						
Mean (SD) from baseline to W4						
Mean (SD) from baseline to W8						
Mean (SD) from baseline to W12						
Mean (SD) from baseline to W24						
Mean (SD) from baseline to W36						
Mean (SD) from baseline to W48						

TABLE 10: QUALITY OF LIFE DIMENSIONS: MOBILITY AND SELF- CARE

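### SAP 10.1.4 and Table 8 analyse two of the three causes in a defined secondary endpoint: medication changes for baseline resistance mutations are left out

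*Combined protocol and SAP*

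**What the plan says.** SAP 2.2.2 lists the secondary endpoint as "Discontinuation or modification of study medication due to insufficient virological response, resistance mutations at baseline, or resistance mutation development before week 48". Section 2.4.2 of the protocol names the same three causes in both v1.5 and v5.0.

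The analysis section, SAP 10.1.4, is narrower. Its heading reads "discontinuation or modification of study medication due to insufficient virological response or resistance mutation development before week 48", and its endpoint statement names the same two causes. The component analyses follow suit: "The analyses will also be performed separately for each component of the endpoint (insufficient virological response and resistance mutation development"). The row in the Table 8 shell reads "discontinuation or modification of study medication due to insufficient virological response or resistance mutations development before week 48", with one sub-row for each of those two causes.

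Protocol 6.1.3 describes what may happen when resistance results arrive after randomisation. For the darunavir (DRV) resistance patterns in its Table 1, "Patients randomised to the DRV arm may be considered to switch to the BIC arm". For the reverse-transcriptase patterns in its Table 2, patients in either arm may stay on their regimen or move to an alternative. For primary integrase mutations, sites are told to consult the study team.

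**The concern.** The SAP defines an endpoint in one section and analyses a different one in another. A statistician who programs from 10.1.4 and Table 8 will not produce the quantity that 2.2.2 promises, and a reader of the report will not know that a cause was dropped.

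The dropped cause is a real pathway in this trial. Treatment may start before the resistance result is known, so some regimen changes will be prompted by virus that was resistant from the outset. Those changes belong to the defined endpoint. Under 10.1.4 the affected patients stay in the denominator as non-events unless they also meet one of the other two causes. One of the routes also exists in one arm only, so the omission need not be neutral between arms.

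**Working it through.** The plan gives no figure for this endpoint, so the check is mainly a comparison of text.

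**1. Causes defined against causes analysed**

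| Place | Insufficient response | Baseline mutations | Mutations that develop |
|---|---|---|---|
| Protocol 2.4.2 (v1.5 and v5.0) | yes | yes | yes |
| SAP 2.2.2 | yes | yes | yes |
| SAP 10.1.4 heading, endpoint, summary, percentage, model | yes | no | yes |
| SAP 10.1.4 component analyses | yes | no | yes |
| SAP Table 8 | yes | no | yes |

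Three causes are defined and two analysed. The omission is consistent, so it is not a slip in one sentence.

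**2. Version lag.** The summary of changes for v1.4 to v1.5 records "additional wording regarding resistance mutations at baseline as patients may switch treatment due to resistance testing results or discontinue medication completely", so the cause was added on purpose. The SAP preface says "The analyses described are based upon the clinical study protocol Version 2.0 dated 16 June 2020", which is later than v1.5. Protocol v5.0 still carries the cause, and no listed change removes it.

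**3. Can the cause occur?** Yes. Appendix 1 of protocol v5.0 does not require the local resistance result before randomisation. The pool is limited, however. Known resistance is an exclusion (5.2, criterion 4), and qualifying results that arrive before randomisation make the patient a screen failure (6.1.3). Only late results count, and a change after a late result is discretionary.

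**4. Is it counted elsewhere?** Not with its reason.
- SAP 10.1.1 covers changes for toxicity, drug interactions and IRIS.
- Table 1B describes baseline mutations, not the changes they cause.
- The deviation table in SAP 6.2 would show receipt of the other arm's treatment, without the reason.
- The patient listing in 10.1.4 gives reasons, but only for patients who meet the two-cause event.

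**5. Effect on the proportion.** The denominator is the whole ITT population either way. The patients who meet any of three causes include all who meet either of two. So in each arm the two-cause proportion is less than or equal to the three-cause proportion.

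**6. Effect on the odds ratio (illustration only).** All event counts here are assumptions. With 220 per arm, and a and b events in the bictegravir (BIC) and DRV arms, OR = [a/(220 − a)] / [b/(220 − b)]. Start from equal events for the two retained causes (OR 1.00), then add baseline-resistance changes:
- 11 retained events per arm, 2 added in the DRV arm only: (11/209)/(13/207) = 0.84. With 11 added: (11/209)/(22/198) = 0.47.
- 44 retained events per arm, 2 added in the DRV arm only: (44/176)/(46/174) = 0.95. With 11 added: (44/176)/(55/165) = 0.75. The 44 is 20% of 220, from the virological failure rate cited in the sample-size section. It is a high value, because some failures are seen only at week 48.
- The same number added in both arms: 1.00.
- 11 retained events per arm, 4 added in the BIC arm only: (15/205)/(11/209) = 1.39.

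The result depends entirely on the assumed number and split. The documents supply neither.

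**The case against.** The strongest reply is that this is a drafting inconsistency in one of several other secondary endpoints, in a SAP at version 0.3 that section 5.1 allows to be updated before sign-off. The two-cause endpoint is coherent in itself. Part of the lost information also appears elsewhere: SAP 6.2 tabulates receipt of the other arm's treatment, and Table 1B shows baseline resistance by arm. All of this is fair, and it limits the importance of the point. It does not remove the mismatch, because none of those tables links a regimen change to baseline resistance.

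A reader might also infer more than the documents support, in two ways.

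- **That the odds ratio is biased, in a known direction.** The two-cause odds ratio estimates a narrower endpoint; that is a departure from the definition, not a demonstrated bias. The DRV-to-BIC route covers Table 1 patterns only. Table 2 patterns apply to both arms, and the action after an integrase mutation is left to consultation. The documents do not say which patterns will be more common.
- **That the omitted events rival those retained.** If 1% to 5% of patients had qualifying baseline resistance (an assumption), 440 × 0.01 = 4.4 and 440 × 0.05 = 22, so about 4 to 22 patients. That is a ceiling, for the reasons in step 3 of the working. No document gives an expected count for the other two causes, so there is nothing to compare it with.

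**Conclusion.** The mismatch is established from the text alone and rests on no assumption: SAP 10.1.4 and Table 8 do not analyse the endpoint that SAP 2.2.2 and protocol 2.4.2 define. As written, the reported proportion could understate the defined one in either arm, and the odds ratio belongs to a different endpoint. Because one route is specific to the DRV arm, the two odds ratios may differ. Neither the size nor the direction of that difference can be derived from the documents, and the illustrative values above should not be read as estimates. The primary analysis, the non-inferiority conclusion and the sample size do not depend on this endpoint. It is worth correcting before the SAP is signed.

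**What to change.** Restore the baseline-mutation cause, in the wording of SAP 2.2.2, in the heading, endpoint, summary, percentage, model and component list of SAP 10.1.4. Add it to the Table 8 row and as a separate component row reported by arm. If the narrower endpoint was intended, the alternative is to remove the cause from SAP 2.2.2, say why, and record the departure from the protocol.

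The cost is some wording and one table row. Reasons for stopping medication are already recorded on the CRF (protocol 6.5), and 10.1.4 already plans to list reasons for stopping or modifying it. There is one small downside. The composite would then include discretionary changes, in an open-label trial, driven by virus present before randomisation and made under partly arm-specific rules. These could shift the odds ratio without reflecting a treatment effect. The separate row lets a reader see how much of any difference comes from that source. No change to clinical management is involved.
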